6.1.6. Pooling of Sites

Sites will not be pooled for analysis.

6.1.7. Derived Variables

6.1.7.1. General

- **Age** = Integer difference in years between the subject's date of informed consent and date of birth.
- **Change from Baseline to Visit X in Parameter Y** = Value at Visit X minus the value at Baseline (as defined in Table 2).
- **Percent Change from Baseline to Visit X in Parameter Y** = Change from Baseline to Visit X in Parameter Y divided by the value at Baseline (as defined in Table 2) multiplied by 100.
- **Shift from Baseline to Visit X in Parameter Y Categories** = Cross-tabulation of below the lower limit of the normal range, within the limits of the normal range, and above the upper limit of the normal range at Baseline (as defined in Table 2) versus at Visit X.
- **Height (cm) and Weight (kg)** = Height (cm) will be calculated as height (in) times 2.54. Weight (kg) will be calculated as weight (lb) times 0.4536.
- **Temperature (C°)** = Temperature (F°) -32 times 5 divided by 9.
- **Treatment duration** = Days in study (date of last Visit minus date of Visit 2 (Baseline)).
- **Days of exposure** = Date of Visit 14 (End of Treatment) minus date of Visit 2. [In the case Visit 14 is missing then the date of study completion will be used.]
- **PH94B use** = average weight of all 6 vials when dispensed – weight of all 6 vials when returned at subsequent visit, at each visit.

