### 9.9.1 Dispensing

At each visit from Visit 2 (Baseline) through the final monthly visit (Visit 13), subjects will be dispensed a monthly kit containing a sufficient number of PH94B Nasal Spray vials from the respective clinical site. Each study site will be provided with an appropriate supply of IP, and each vial will be individually numbered with a unique identification code.

Prior to the subject receiving the IP at each in-clinic visit, the Investigator or study staff will use a vial from their assigned kit to instruct the subject on how to ensure the IP is primed before use according to instruction. At least 1 vial of the IP will be primed at each clinic visit following Visit 2 (Baseline) as needed. The IP will be weighed prior to priming, and again when returned to study staff. Once primed the IP must be stored at room temperature.

Subjects should use a fresh vial at the start of each week. Subjects will be instructed to remove the new vial from their home refrigerator, bring it to room temperature and prime the spray actuator before use as needed. The clinic will dispense a kit of vials with unique serialized vial identification codes at each visit.

If the IP supply is lost or depleted prior to next in-clinic visit, subjects may notify the study site through the provided study site phone number to secure additional supply of IP.

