Subjects will be instructed to return to the clinic for Visit 3 after 30 days (± 3 days). At Visit 3, subjects will undergo clinical laboratory assessments (clinical chemistry, hematology, urinalysis, pregnancy test, and urine drug screening), vital signs, 12-lead ECG, physical examination, HAM-D17, [REDACTED] LSAS, C-SSRS, CGI-S, CGI-I, and self-evaluation by the patient-reported outcome measure, Patient Global Impression of Change (PGI-C). At Visit 3, PH94B use recorded in the eDiary application will be reviewed and AEs and concomitant medications will be reported and recorded. Subjects will receive a 1-month supply of PH94B (6 vials).

Subjects will return to the clinic at monthly intervals (± 7 days, Visits 4 to 13), and will repeat the same assessments as those performed at Visit 3. PH94B use recorded in the eDiary application will be reviewed, AEs and concomitant medications will be reported and recorded, and at each Visit subjects will receive a 1-month supply of PH94B (6 vials).

At Visit 14 (1 year ± 2 weeks), treatment will conclude, and subjects will undergo clinical laboratory assessments (clinical chemistry, hematology, urinalysis, pregnancy test, and urine drug screening), vital signs, 12-lead ECG, physical examination, HAM-D17, [REDACTED] LSAS, C-SSRS CGI-S, CGI-I, and PGI-C. Also, PH94B use recorded in the eDiary application will be reviewed, and AEs and concomitant medications will be recorded and reported. Subjects will also be informed of their follow-up Visit (Visit 15).

Subjects will return to the clinic for a follow-up Visit (Visit 15, 54 weeks ± 3 days), approximately 2 weeks after the last PH94B administration, to undergo C-SSRS and vital signs assessments, and record AEs.

Safety Considerations:

Safety and tolerability of PH94B (≤ 4 doses per day up to 12 months in up to 600 subjects) will be assessed and summarized through changes from baseline (Visit 2) to end of treatment (Visit 14) in AEs, laboratory values, 12-lead ECGs, physical examinations, and vital sign assessments following exposure to PH94B.

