7.4. Exposure

PH94B will be supplied in [REDACTED] Each spray delivers 1.6 µg per 100 µL spray. At Visit 2 (Baseline) and each monthly Visit thereafter, site personnel will instruct the subject to self-administer the IP by 1 spray into each nostril (right and left nasal passages), for 2 total sprays per dose up to 4 times per day.

Number of days of exposure to PH94B (date of Visit 14 (or completion date) minus date of Visit 2 (Baseline)) will be summarized overall. Average difference in vial weights at each visit (for all subjects completing each visit) will be summarized overall.

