14.1 Demographic Data Summary Tables and Figures		
Table 14.1.1.1	All Subjects	Subject Enrollment and Disposition
Table 14.1.1.2	All Subjects	Protocol Deviations
Table 14.1.2.1	Safety	Demographics and Baseline Characteristics
Table 14.1.3	Safety	Medical and Psychiatric History by System Organ Class and Preferred Term
Table 14.1.4	Safety	Prior Medications by ATC Class and Preferred Term
Table 14.1.5.1	Safety	Exposure to Investigational Product
Table 14.1.5.2	Safety	PH94B Use by Study Visit

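### The SAP's vial-weight definition of PH94B use cannot be applied as written and yields no doses per day, so the dose summaries of Protocol 13.1.3 drop out without being listed as a change

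*SAP*

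**What the plan says.** SAP 6.1.7.1 defines PH94B use as "average weight of all 6 vials when dispensed – weight of all 6 vials when returned at subsequent visit, at each visit". SAP 7.4 adds: "Average difference in vial weights at each visit (for all subjects completing each visit) will be summarized overall". The result feeds planned Table 14.1.5.2, titled "PH94B Use by Study Visit". For Visit 3, SAP Section 3 states "Subjects will receive a 1-month supply of PH94B (6 vials"), and it repeats that count for Visits 4 to 13. The supply wording for Visit 2 is blacked out.

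Protocol 9.9.1 (Version 2.0, which the SAP says it follows) gives no vial count: "subjects will be dispensed a monthly kit containing a sufficient number of PH94B Nasal Spray vials". It also says "Subjects should use a fresh vial at the start of each week". If supply is lost or runs out between visits, subjects may call the site "to secure additional supply of IP". On weighing: "The IP will be weighed prior to priming, and again when returned to study staff".

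Protocol 13.1.3 plans to summarise total doses and average daily doses, overall and for four 3-month periods. SAP 7.4 has days of exposure and vial-weight differences, each overall only. SAP Section 10 drops the exploratory use-pattern objectives because the eDiary data were unreliable, and does not mention 13.1.3. SAP Section 5 says adverse events will be grouped by length of exposure and level of use. SAP 8.1 splits treatment-emergent events only around Visit 14.

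**The concern.** Safety is the primary objective, the sample size was chosen to build a safety database, and the drug is taken as needed. Days of exposure are calendar days between two visits, whether or not any drug was used. Daily dose counts were to come from the eDiary (Protocol 9.4.1), which the SAP calls unreliable. Vial weight is then the main remaining evidence on how much drug subjects used.

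As defined, that measure needs a programmer to guess what is meant, and it mixes amount used with interval length and priming. A safety report could then say how long subjects were in the study, but not how many doses a day that time represents.

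**Working it through.** The plan gives no figure of its own to reproduce.

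**Inputs.** One spray is 100 µL and a dose is two sprays, so 0.2 mL (Protocol 9.1 and 9.2). A vial holds 8 mL (Protocol 9.1). The maximum is 4 doses a day (Protocol 9.2). Visits 4 to 13 have a ±7-day window (Protocol 10.2). Assumptions: solution density 1 g/mL and a 30-day month; the documents give no density.

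**1. Literal reading.** Let W be the gross weight of a full vial and U the weight of drug removed from six vials. The formula gives W − (6W − U) = U − 5W. The contents of five vials alone are 5 × 8 = 40 mL. Maximum use over 30 days is 4 × 30 × 0.2 = 24 mL. The result is negative at every permitted level of use, at any density, and the glass makes it more so.

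**2. Kit total or per-vial mean.** The summed difference is 6W − (6W − U) = U. The per-vial mean difference is U/6. The ratio is 6 at every level of use. For a reported 4.0 g over 30 days:
- as a kit total: 4.0 / 0.2 = 20 doses, and 20 / 30 = 0.67 a day;
- as a mean over six vials: 4.0 × 6 = 24 g, 24 / 0.2 = 120 doses, and 120 / 30 = 4 a day, the protocol maximum.

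**3. No division by days.** The protocol does not say whether windows run from Baseline or from the previous visit. From Baseline, consecutive visits can be 30 − 14 = 16 to 30 + 14 = 44 days apart; from the previous visit, 23 to 37 days. One subject at a constant 2 doses a day uses 2 × 0.2 = 0.4 g a day:
- from Baseline: 16 × 0.4 = 6.4 g to 44 × 0.4 = 17.6 g;
- from the previous visit: 23 × 0.4 = 9.2 g to 37 × 0.4 = 14.8 g.

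**4. Priming.** With a fresh vial each week, 30 days opens 5 vials. Each priming spray per vial adds 5 × 0.1 = 0.5 mL, the volume of 0.5 / 0.2 = 2.5 doses, or 2.5 / 30 = 0.08 doses a day. That is 0.5 / 6 = 8% of true use at 1 dose a day and 0.5 / 24 = 2% at 4 a day. The current protocol refers to separate instructions and gives no number of priming sprays, so the total cannot be calculated.

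**5. Protocol against SAP.** Protocol 13.1.3 needs total doses, doses per day and four 3-month periods. None of these appears in SAP 7.4 or in the titles of planned Tables 14.1.5.1 and 14.1.5.2. Section 10 lists the removal of exploratory objectives; the 13.1.3 summaries are exposure summaries, not exploratory objectives.

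**6. Level of use.** Protocol 13.1.5.1 separates users at 3 or 4 times a day from those at 2 or fewer. The SAP does not adopt this split for the Section 5 grouping, and a weight without a dose and day conversion cannot supply it.

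**The case against.** The best defence is that the intended meaning can be recovered. SAP 7.4 speaks of an average difference over subjects completing each visit, and the six-vial phrase appears on both sides of the definition. The natural reading is kit weight out minus kit weight back, averaged across subjects. This stands in part: a reader might infer that the report will probably be wrong six-fold, and the documents do not support that. The six-fold gap is an ambiguity between two possible readings, and the per-vial reading is the less supported one. The text still does not settle it.

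Other points that stand:
- The protocol's open vial count does not contradict six; a kit may well hold six. The weakness is that the SAP fixes a count the current protocol does not, with no rule for extra supply.
- The window figures are extremes for an individual. In visit means the variation partly averages out.
- A reader might infer that the dose summaries were dropped silently. Section 10 discloses the eDiary problem, which is the likely reason. What is missing is the statement that 13.1.3 is affected and that vial weight takes the place of dose counts.
- A reader might infer that no level of use is defined anywhere. Protocol 13.1.5.1 defines one.
- The interim milestones in Protocol 13.1.6 are counted by duration of dosing, which days of exposure address.
- The table shells are not in the text available for this review and could state units or a conversion.

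**Conclusion.** The point holds and should be fixed, as a defect in how amount of use is measured. The definition is unusable literally. The sensible repair leaves a six-fold choice open. The vial count is fixed without support in the current protocol, priming is included, and the visible text gives no route to doses per day. The summaries in Protocol 13.1.3 are therefore lost, and Section 10 does not list that change.

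It would be wrong to infer that the main safety results are compromised. The adverse event subject counts in SAP 8.1 and the days of exposure do not use this variable. The gram figures assume 1 g/mL and a 30-day month; the six-fold ratio needs only the six vials.

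**What to change.** In SAP 6.1.7.1 and 7.4:
- For each visit interval, define use as summed dispensed weight minus summed returned weight over all vials actually dispensed, matched by vial code and including extra supply.
- Divide by the weight of one 0.2 mL dose, stating the density, and by the days in the interval.
- Treat an interval with an unreturned vial as missing, report how many there are, and note that non-return may be related to use.
- State that priming is included, and give a sensitivity range for a priming allowance per opened vial. A vial that lost weight can be taken as opened.
- Report approximate total and mean daily doses, overall and by 3-month period.

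In Section 10, list the change of source from eDiary to vial weight. For Section 5, apply the Protocol 13.1.5.1 split to mean doses per day, saying where a mean between 2 and 3 falls, or delete the sentence.

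The cost is SAP wording and modest programming. Vial weights (Protocol 9.4) and vial codes (Protocol 9.11.1) are already recorded in the eCRF. The density has to be obtained, and the priming count obtained or covered by the sensitivity range. The downside is that dose figures are approximate and are lost for intervals with unreturned vials.

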6.1.7.1. Clinical Global Impression Scale of Improvement (CGI-I)

The CGI-I is a clinician-rated instrument that measures the clinician's evaluation of change in subjects' overall improvement with treatment on a scale where 1 = "Very much improved" and 7 = "Very much worse." In this study, the CGI-I will be completed by the study investigator at each monthly Visit to the clinic.

The derived variable from this assessment will be the following:

- **Proportion CGI-I Responders** = Proportion of subjects with a score of 1 (Very much improved) or 2 (Much improved) on the CGI-I.

6.1.7.2. Patient Global Impression of Change (PGI-C)

The PGI-C is a self-administered instrument that measures change in subjects' overall improvement with treatment on a scale where 1 = "Very much improved" and 7 = "Very much worse." Subjects will rate their impression of change at each monthly visit to the clinic.

The derived variable from this assessment will be the following:

- **Proportion PGI-C Responders** = Proportion of subjects with a score of 1 (Very much improved) or 2 (Much improved) on the PGI-C.

6.1.7.3. Liebowitz Social Anxiety Scale (LSAS)

The LSAS is a clinician-rated scale that has been shown to be sensitive to treatment-related change in social phobia symptoms. The time frame for rating symptomatology is the past week. Note, there (instead of these) are monthly Visits to the clinic. The scale consists of 24 items. Each item is given 2 ratings: fear or anxiety on a scale of 0 to 3 and avoidance on a scale of 0 to 3, with a total maximum overall score of 144. The total LSAS score for each subject is the sum of all ratings across both scales. The derived variable for this assessment is change from the LSAS baseline (Visit 2 [Baseline]) at each monthly Visit in total LSAS rating.

6.1.7.4. Hamilton Depression Scale (HAM-D)

At Visit 1 (Screening) and each monthly Visit, subjects will be asked to complete the clinician-rated HAM-D questionnaire to assess depression. The HAM-D questionnaire consists of 17 items, each scored on either a 3- or 5point scale.

The Hamilton Depression Scale (HAM-D) total score is calculated as the sum of the 17 individual item scores and ranges from 0 to 52.

6.1.7.5.

[REDACTED] (HAM-A) total score is calculated as the sum of the 14 individual scores, ranging from 0 to 56.

6.1.8. Data Adjustments/Handling/Conventions

All collected data will be presented in listings. Data not subject to analysis according to this plan will not appear in any tables or graphs but will be included only in the data listings.

Medical history and AEs (all types) will be coded using the most recent version of the Medical Dictionary for Regulatory Activities (MedDRA), version 25.1. Prior and concomitant medications will be coded using the World Health Organization Drug Dictionary (WHO-DD) Anatomical Therapeutic Chemical (ATC) classes and preferred terms, version WHODrug B3 Global Sep 2021.

If partial dates occur, the convention for replacing missing dates for the purpose of statistical analysis is as follows: if just day is missing then the day assigned is the first day of the month or the date of first dose (if in the same month), whichever is later; if just month is missing then the month assigned is the month of the first dose, unless that results in a date before the first dose in

which case the month after the first dose is used; and if both month and day are missing then the month assigned is the month of the first dose and the day assigned is either the first day of the month or the first dose date, whichever is later.

If partial times occur, the convention is as follows: if the missing time occurs on the day of the first dose and both the hour and minute are missing then the time assigned is the time of the first dose, otherwise if both the hour and minute are missing and the date is not the date of first dose the time assigned is 12:00; if the date is the same as the date of the first dose and only hour is missing the hour assigned is 12 or the hour of first dose, whichever is later, and if the date is the same as the date of first dose and only the minute is missing the minute assigned is 30 or the minute of first dose, whichever is later. Otherwise the hour assigned is 12 if the hour is missing and the date is not the same as the date of first dose and the minute assigned is 30 is the the date is not the same as the date of first dose.

These conventions will be applied only to AE and medication onset dates and times with the following precaution: if the missing date and time reflect the date and time of onset of an AE, the modified date and time will be constructed to match the first documented date/time post drug administration while preserving the order in which the AE/medication was reported in the eCRF.

7. Study Subjects and Demographics

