### 13.1. Statistical Analysis

This section presents a summary of the planned statistical analyses.

Safety, tolerability, and efficacy variables will be summarized using descriptive statistics. Descriptive summaries for categorical variables will include count and percentage. Descriptive summaries for continuous variables will include number of subjects (n), mean, standard deviation (SD), median, minimum, and maximum. Where appropriate, 95% confidence intervals (CIs) may be reported. Summaries will be presented by time point. All CIs will be 95%, unless stated otherwise.

Unless specified otherwise, all data recorded, will be listed by subject. A comprehensive description of planned analyses and statistical considerations will be described in the statistical analysis plan (SAP).

Summary statistics will be reported based upon observed data. Should a determination of treatment period be required for an AE or concomitant medication when the corresponding date is missing, or is a partial date, the event/medication will be considered as “on-treatment” unless the portions of the date that are available indicate that this is not possible.

Details of the planned analyses, including strategies if needed to assess and address consequences of the COVID-19 pandemic on study conduct and study data, will be provided in the SAP that will be finalized before the database is locked.

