8.1. Adverse Events

Treatment emergent AEs (TEAEs) are defined as:

- AEs with onset at the time of or following the start of treatment with IP through final Visit or follow-up phone call.
- AEs starting prior to the start of treatment with IP but increasing in severity or relationship at the time of, or following, the start of treatment with IP through Visit 14 (End of Treatment/Follow-Up).
- AEs that occur between Visit 14 and Visit 15.

Any medical condition that is present at the time that the subject is screened will be considered as baseline and not reported as an AE. However, if the study subject's condition deteriorates at any time during the study, it will be recorded as an AE.

The Investigator will record all reportable events with start dates occurring any time after informed consent is obtained until 7 days after the last day of study participation. Events will be followed for outcome information until resolution or stabilization. Missing and partially missing start dates will be imputed for the purpose of analysis as described in Section **Error! Reference source not found.**

All AEs, TEAEs, and serious AEs (SAEs) will be coded using the MedDRA dictionary, as discussed in Section **Error! Reference source not found.**

All AE data will be categorized as Severe > Moderate > Mild. Relationship of all AEs to IP will be categorized as related or not related. In the summaries showing severity and relationship to study drug, the event with the maximum severity or strongest relationship to study drug will be reported. If a particular event is missing the severity and/or relationship, then the strongest possible severity or relationship will be assumed for analysis (severity = severe, relationship = related).

An overall summary of TEAEs will be provided; this will present number and percent of subjects who reported at least 1 of the following: TEAE (including any TEAE, TEAEs by maximum severity, and related TEAEs), TEAE leading to discontinuation of the study drug, TEAE leading to discontinuation from the study, serious TEAEs, and SAEs leading to death. TEAEs will be summarized by two time periods (TEAEs which occur prior to Visit 14 and those that occur during or after Visit 14).

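### SAP 6.1.8 gives an onset with a missing month the month of first dose without regard to the recorded year and with no cap at study exit, and its separate AE sentence conflicts with that rule.

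*SAP*

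**What the plan says.** SAP 6.1.8 treats three kinds of partial date.

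- Day only missing: the recorded month and year are kept. This part causes no difficulty.
- Month only missing: "if just month is missing then the month assigned is the month of the first dose". The one exception is a result that precedes first dose, in "which case the month after the first dose is used". Nothing is said about the year.
- Month and day missing: "month assigned is the month of the first dose and the day assigned is either the first day of the month". The alternative is the first dose date, and the later of the two is taken. It is not stated whether the first dose date here means a whole calendar date or a day of the month.

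On scope, the section says: "These conventions will be applied only to AE and medication onset dates and times". It then adds a precaution for AE onsets: the constructed date and time should coincide with the first one documented after dosing, keeping the order in which events were reported. How the precaution ranks against the rules above is not stated.

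Protocol 13.1 works differently. An event or medication with a missing or partial date counts as on-treatment "unless the portions of the date that are available indicate that this is not possible".

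The imputed onset is used in SAP 8.1, where the treatment-emergent (TEAE) window closes at the final visit or follow-up contact and the summaries separate "TEAEs which occur prior to Visit 14 and those that occur during or after Visit 14". Medication start dates feed the prior and concomitant classes in SAP 8.5. SAP section 10, which lists changes from the planned analysis, does not mention a change to the partial-date rule.

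**The concern.** Treatment lasts up to 12 months, so participation can span two calendar years. For an AE in the second of those years, the year is informative and the month of first dose is not. Combining the recorded year with the first-dose month puts the onset close to the first anniversary of dosing, wherever it really fell. For a subject who stopped early, that is a date on which the subject was no longer under observation.

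AEs are the primary outcome, and their onset dates determine both TEAE status and period. A misplaced onset can remove a true on-treatment event from the TEAE tables or put it in the period during or after Visit 14. Because two sentences in the section compete, two programmers could also produce different tables from the same data.

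**Working it through.** The documents give no figure on this point, so there is none to reproduce. The check applies the rule to dates.

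**Inputs.** Imputation rule: SAP 6.1.8. Treatment up to 12 months, early termination possible: Protocol 2.1 and 7.1. Visit 14 at 52 weeks ± 2 weeks, that is 364 ± 14, or days 350 to 378; Visit 15 at 54 weeks ± 3 days, at latest 378 + 3 = day 381: Protocol Table 2-1. The subject dates are illustrative assumptions.

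**Two readings when month and day are missing.** Reading A keeps the recorded year and treats the first dose date as a day of the month. Reading B compares whole dates and takes the later.

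**Example.** First dose 10 November 2022; exit 8 February 2023 (20 + 31 + 31 + 8 = day 90); AE recorded only as 2023.

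- Reading B: 1 November 2023 = 365 − 9 = day 356, which is 356 − 90 = 266 days after exit.
- Reading A: 10 November 2023 = day 365, which is 275 days after exit.
- Day 25 and year known, month missing: 25 November 2023 = 365 + 15 = day 380, past the latest Visit 14 (day 378).

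**Range.** Over all first-dose dates in a three-year span, a following-year onset is placed at day 335–366 (reading B), 365–366 (reading A) or 335–396 (month only missing). The minimum is 335, so anyone whose last contact was earlier has every such AE placed after exit.

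**By length of follow-up.** Assume first doses spread evenly over a year and onsets spread evenly over follow-up. The share of onsets falling in the following calendar year is then about (last contact ÷ 2) ÷ 365.

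| Last contact | Onsets in following year | Of these, placed after last contact: month and day missing | Month only missing |
|---|---|---|---|
| Day 90 | 12% | 100% | 100% |
| Day 180 | 25% | 100% | 100% |
| Day 270 | 37% | 100% | 100% |
| Day 330 | 45% | 100% | 100% |
| Day 378 | 52% | 0% | 13% |

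These are shares of onsets that would be exposed if their month were missing. They are not shares of AEs expected to be wrong.

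**Visit 14 split.** Even for completers, days 335–366 overlap the Visit 14 window (days 350–378). An AE from the middle of treatment can be placed after Visit 14.

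**If the AE precaution governs.** The example AE goes to the start of dosing in November 2022, although the record says 2023. It stays treatment-emergent, but the date is impossible, and an event that truly arose after Visit 14 would move to the earlier period. The error can also run the other way. With first dose 10 January 2023 and a screening AE recorded only as 2022, the precaution makes the AE treatment-emergent, whereas Protocol 13.1 would not.

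**Medications.** First dose 15 June 2022, drug start recorded only as 2015: reading A gives 15 June 2015 (still pre-study), reading B gives 15 June 2022. First dose 10 November 2022, drug started 15 January 2022 and recorded only as 2022: both readings give 10 November 2022, a shift of 299 days.

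**The case against.** The strongest reply is that the AE precaution, read naturally, qualifies the general rule for AEs. If it governs, none of the day-356 or day-365 dates arise. That is correct, and those figures are conditional on the general rule applying. It does not rescue the section, because the precaution produces a date that contradicts the recorded year.

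A second reply is that the trigger is rare. AEs are asked about at each visit, visits are monthly, the case report form asks for start date and time, and queries must be resolved (Protocol 11.2, 11.2.3, 14.5.2). An on-study AE with only a year, or with day and year but no month, should be uncommon. All AEs are listed and no inferential test depends on these dates. This stands and limits the size of the point.

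A reader might infer that the rule also turns pre-study drugs into on-study starts because it ignores the year. The documents do not support that in general. An earlier-year drug moves only if the first dose date is read as a whole date, or if the month after first dose is read as a specific calendar month. The same-year shift comes from the first-dose default, not from ignoring the year, and Protocol 13.1 would also call such a drug on-treatment. Under SAP 8.5 a drug taken before Visit 2 counts as prior, and one that continues is concomitant in any case, so at most the prior flag is at risk.

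Nor does the SAP say that the recorded year is to be disregarded. It is silent on the year.

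**Conclusion.** The point holds for AE onsets. The rule lacks a year condition and an upper cap, the precaution conflicts with it, no order of precedence is given, and the protocol's reliance on the recorded date parts has been lost without being declared. Under the general rule, every following-year AE with a missing month is dated after exit for a subject who left before about day 335. For a subject followed to day 378, post-exit dates arise only when the month alone is missing (13% of following-year onsets under the even-spread assumption), although the Visit 14 split can still be affected. Under the precaution, onsets move to the start of dosing against the recorded year.

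The number of partial dates is unknown and probably small, so no effect on a TEAE percentage can be stated. It would overstate the matter to say that the primary safety tables will be wrong. What the documents support is that the rule, under either sentence, gives wrong dates for the records it reaches. It should be corrected before programming.

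**What to change.** For AE onsets, replace the month rules with one conditioned on the recorded parts:

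- If the recorded parts show onset before first dose, keep the AE pre-treatment.
- If they are compatible with the year (or month) of first dose, assign the first dose date, or the earliest compatible date on or after it.
- If the recorded year is later, assign the earliest date compatible with the recorded parts.
- Always cap at the AE end date and last study contact.

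In the example this gives 1 January 2023, day 52 (20 + 31 + 1), inside the 90 days of participation. The earliest compatible date is never later than the true onset, so no on-study AE can be placed after exit. A simpler floor at the first dose date would not do. AEs are recorded from consent, so an AE dated October 2022 with first dose on 10 November 2022 would be pulled into the treatment period, against Protocol 13.1.

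Delete the precaution, or state that it is subordinate to this rule.

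For medications, keep the recorded year so that earlier-year drugs stay prior. For same-year partial dates, set prior status from whether the drug was recorded as taken before Visit 2, not from the imputed date.

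The cost is SAP wording and a minor programming change.
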